## **Research question and objectives**

**Research question:** “Is exposure to siponimod therapy during pregnancy associated with an increased risk of adverse pregnancy or infant outcomes?”

To answer this research question, the investigators will monitor pregnancy and infant outcomes in women in the US and Canada exposed to siponimod during pregnancy.

### **Objective:**

The primary objective is to estimate and compare the prevalence of major structural defects in siponimod exposed pregnant women versus 1) disease-matched pregnant women not exposed to siponimod, and 2) healthy pregnant women.

Secondary objectives are to estimate and compare the prevalence of selected adverse pregnancy and infant outcomes in siponimod-exposed pregnant women versus 1) disease-matched pregnant women not exposed to siponimod, and 2) healthy pregnant women.

The primary outcome of the study is major structural defects.

The secondary outcomes of the study are:

- Spontaneous abortion
- Stillbirth
- Elective termination
- Preterm delivery
- Preeclampsia / eclampsia
- Small for gestational age infants
- Small for age for postnatal growth to one year of age
- A pattern of minor structural defects
- Developmental performance at approximately one year of age
- Serious or opportunistic infections in the first year of life.

### **Study design**

This study will utilize a prospective, observational, exposure cohort design to examine pregnancy and infant outcomes in women and infants who are exposed to siponimod during pregnancy to treat MS. The prevalence of each outcome in women exposed to siponimod and their infants will be compared to those observed in two unexposed comparator groups: a disease-matched comparison group of women who have not used siponimod during pregnancy (unexposed disease-matched comparison group), and a comparison group of healthy women who do not have diagnosis of MS, have not had exposure to a known human teratogen, and have not taken siponimod in pregnancy (healthy comparison group). Pregnant women exposed to siponimod who do not meet the prospective cohort criteria will also be followed as part of an exposure series. All participants will be recruited via voluntary participant registration following informed consent by the pregnant woman for her participation. Participants may withdraw from the study at any time.

An interim feasibility assessment will be performed by the Sponsor after three years from Registry initiation to ensure that the study can meet the sample size requirements within a reasonable timeframe to address the scientific question of interest (i.e. within 10 years from registry initiation). This interim assessment will consider data from the Registry and all available data sources such as real-world evidence studies, pharmacovigilance and marketing.

### **Setting and study population**

The study population includes pregnant women who reside in the US or Canada.

Three cohorts of women will be enrolled prospectively into the cohort study and followed for pregnancy and infant outcomes:

- Siponimod-Exposed Cohort: Pregnant women with MS exposed to siponimod during pregnancy (i.e. on or any time after the 4th day post the first day of LMP prior to conception) (N = 289)
- Disease-Matched Comparison Cohort: Pregnant women with MS not exposed to siponimod during pregnancy (N = 289)
- Healthy Comparison Cohort: Pregnant women who are neither diagnosed with MS nor with any other autoimmune disease, and not exposed to siponimod or any known teratogenic agent during pregnancy (N = 289)

The term “exposed to siponimod” is used here as synonym to “administered siponimod”.

Using the multi-product registry concept, this Mayzent-OTIS pregnancy registry (BAF312A2403), will be leveraged for the Kesimpta-OTIS pregnancy registry sub-study (OMB157G2403). Considering the identical population (inclusion/exclusion criteria) and design, the Kesimpta-OTIS sub-study will use the contemporaneous Mayzent-OTIS pregnancy registry comparator cohorts.

The ‘Disease-Matched Comparison Cohort’ and the ‘Healthy Comparison Cohort’ will be common between this study and the Kesimpta-OTIS pregnancy registry sub-study (OMB157G2403) study. The first 125 pregnancies in the two comparison groups from the time of the Kesimpta protocol (OMB157G2403) approval will be eligible for inclusion in both studies (i.e., the current study and the Kesimpta-OTIS pregnancy registry sub-study).

Up to an additional 50 women will be enrolled in an exposure series group. This is a group of women with exposure to siponimod during pregnancy, but who do not meet eligibility criteria for the siponimod-exposed cohort group (e.g. retrospective cases would be enrolled in the exposure series group).

## **Variables**

Exposure will be defined as siponimod treatment any time from the first day of the last menstrual period (LMP) prior to conception + 4 days up to and including the end of pregnancy by maternal report and verified by medical record review, with detailed information on the gestational timing, route of administration, dose, and dates of exposure. Outcome variables include major structural birth defects (including interventions for those defects and outcome up to one year of age), spontaneous abortion, stillbirth, elective termination, preterm delivery, minor structural defects, small for gestational age at birth, small for age on postnatal growth at 1 year of age, developmental performance on the Ages and Stages (ASQ) questionnaire for live born infants at 1 year of age, and serious or opportunistic infections in live born infants through the first year of life. Data will be obtained by maternal report, physical examination, and medical record review. Potential confounders or covariates to be collected include maternal age, race/ethnicity, socioeconomic status, body mass index (BMI), pregnancy and health history, lifestyle factors such as tobacco and alcohol use, comorbidities, medication, vaccine and vitamin/mineral exposures, and prenatal tests. Measures of disease severity will be collected for those enrolled in the siponimod-exposed and disease-matched cohorts. Details regarding definitions will be provided in the Statistical Analysis Plan (SAP) to be developed separately.

## Data sources

Data will be collected during maternal interviews and via questionnaires, medical record, pregnancy exposure diary, dysmorphology examination data, and the ASQ. Data will be recorded on hard copies of forms or electronically, and these records will be retained by OTIS. These forms are considered the primary data sources for the study. Data from these forms will be extracted and entered into a customized OTIS study database located in the OTIS Research Center and developed specifically for OTIS studies.

## Study size

The prospective cohort study target sample size is 289 pregnant women who have been exposed to siponimod in pregnancy (i.e. on or any time after the 4th day post first day of the LMP prior to conception), for MS, 289 pregnant women diagnosed with MS not exposed to siponimod during pregnancy (primary comparison group/comparison group 1), and 289 healthy women i.e. women who are not diagnosed with MS, or any other autoimmune disease, and without exposure to siponimod, or any known human teratogen during pregnancy (secondary comparison group/comparison group 2).

The current sample size provides 80% power to detect a risk ratio of approximately 3.0 or greater in major structural defects with reference to the baseline prevalence of 2.8% in the Atlanta metropolitan area ([CDC 2017](#)).

Up to an additional 50 women will be enrolled in an exposure series group. This is a group of women with exposure to siponimod during pregnancy, but who do not meet eligibility criteria for the siponimod-exposed cohort group (e.g. retrospective cases would be in this group).

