The study population includes pregnant women who reside in the US or Canada with siponimod-exposure for the approved indication, and 2 comparison groups without siponimod exposure during pregnancy (1 disease-matched unexposed comparison group, and 1 healthy unexposed comparison group). Since the population under study (i.e. inclusion/exclusion criteria) are the same between this study (BAF312A2403) and the Kesimpta-OTIS pregnancy

registry sub-study (OMB157G2403) and the two studies will run in parallel using the same design, the comparator cohorts will be common between both studies. The first 125 pregnancies in the two comparison groups from the time of Kesimpta protocol (OMB157G2403) approval will be eligible for inclusion in both studies (i.e., the current study and the Kesimpta-OTIS pregnancy registry sub-study).

Based on use of multiple methods for identification and recruitment of exposed women, and the previous recruitment experience of the existing OTIS studies, the investigators have projected that approximately 17-18 pregnant women with exposure to siponimod could be enrolled in the Registry each year, although the true number of exposed pregnancies potentially available for enrollment in the Registry cannot be known at this time.

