### **7.2.1 Study period**

The study is planned for about 10.5 years from the enrollment of the first patient in (FPI) until study completion. There will be 7 years of active recruitment, with an annual interim report reviewed by the Scientific Advisory Board each year. The final report with statistical analysis according to the statistical analysis plan (SAP) will be prepared at the end of the study.

Pregnant women will be followed throughout their pregnancy and pregnancy outcome information will be collected. Live born infants will be followed through one year of age.

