## 7.5 Study size

Recruitment goals are set at an average of 34-36 subjects per year in each of the 3 groups as shown below in [Table 7-3](#), for a total of 867 subjects in the cohort, and an additional up to 50 subjects in the exposure series (anticipated recruitment not shown in the table), over a 7-year recruitment period. Balance in the cohort numbers will be monitored on a monthly basis, and overall balance addressed by adjusting recruitment activities as needed. It is not possible to predict the number of pregnancy exposures that will occur for a newly marketed medication, or that the recruitment rates will be equal in all years, and therefore, sample size is based on estimates that may require revision as the study progresses.

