### 7.5.1 Determination of sample size

The sample size for this study is not only based on the statistical considerations to address the question of interest but also takes into account the feasibility aspects, prior experience and available literature ([Krueger et al 2017](#)) on conduct of pregnancy registries in the MS disease area.

In the three cohorts, approximately 867 pregnant women will be enrolled in US and Canada with a ratio of 1:1:1.

Based on previous experience with MotherToBaby/OTIS Pregnancy Studies, it is estimated that subjects will be an average of 7-10 weeks post-LMP at the time of enrollment. Given this mean gestational timing at enrollment, the anticipated spontaneous abortion/stillbirth rate is 10%, the estimated elective abortion rate is 5%, and the estimated lost to follow-up rate is 5% ([Chambers et al, 2016](#)). This will result in known outcomes for approximately 273 pregnancies in each cohort, including 231 pregnancies with at least one live born infant in each cohort at the end of recruitment.

Baseline rates of major structural birth defects, specific patterns of three or more minor structural defects, premature delivery, and small for gestational age are based on previous MotherToBaby/ OTIS studies and on general population data. Rates of spontaneous abortion in the general population are 15-20% ([Avalos AL, et al 2012](#), and [Magnus et al 2019](#)). However, since women do not typically enroll in pregnancy registries until after 7-8 weeks' gestation when the highest risk of spontaneous abortion has passed, the baseline estimate is drawn from previous OTIS studies. [Table 7-4](#) gives the minimum detectable effect sizes with 80% power (two-sided significance level 0.05, except as noted below for pattern of minor structural defects), for the comparisons described above. If the disease-matched comparison and the healthy comparison groups are comparable, then consideration will be given to pooling data in the two comparisons cohorts for analysis, as shown in [Table 7-5](#). The current sample size provides 80% power to detect a risk ratio of approximately 4.4 or greater in major structural defects compared to the baseline prevalence of 3% in the comparison groups. This is consistent with the population prevalence of major structural defects of 2.8% in the Atlanta metropolitan area ([CDC 2017](#)).

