**Table 7-4 Sample Size and Detectable Effect Size with 80% Power for Comparison of Exposed Cohort 1 to Unexposed Cohort 2**

Endpoint	N per group	Rate in comparison group	Relative risk	Power
Major structural defects b	231	3%	3.0	80%
Specific pattern of 3 or more minor structural defects	231	1%	4.6	80% c
Spontaneous abortion/still birth	259	10%	1.9	80%

Endpoint	N per group	Rate in comparison group	Relative risk	Power
Preterm delivery	231	10%	1.9	80%
Small for gestational age	231	10%	1.9	80%

aAll tests are two-sided with alpha = 0.05, based on Fisher's exact test, unless specified otherwise. Calculations conducted using R.

bPrimary endpoint; among livebirths.

cOne-sided

**Table 7-5 Sample Size and Detectable Effect Size with 80% Power for Comparison of Exposed Cohort 1 to Unexposed Cohorts 2 and 3 Combined**

Endpoint	N in exposed group	N in comparison group	Rate in comparison group	Relative risk	Power
Major structural defects b	231	462	3%	2.7	80%
Specific pattern of 3 or more minor structural defects	231	462	1%	4.0	80% c
Spontaneous abortion/still birth	259	518	10%	1.7	80%
Preterm delivery	231	462	10%	1.8	80%
Small for gestational age	231	462	10%	1.8	80%

aAll tests are two-sided with alpha = 0.05, based on Fisher's exact test, unless specified otherwise. Calculations conducted using R.

bPrimary endpoint; among livebirths.

cOne-sided

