The calculation of frequency of birth defects excludes fetal losses (spontaneous abortions, elective terminations, or fetal deaths) for which no birth defects have been detected as they may introduce a classification bias. It is unknown what percentage of these pregnancies consists of potentially normal outcomes or birth defects. The Registry attempts to obtain information on birth defects detected at the time of the outcome. However, the malformation status of the aborted fetus may not be known. For this reason, the primary comparison for this outcome of the study will be conducted among pregnancies ending in live birth, and a secondary analysis of this outcome will include all pregnancies with known outcome.

It is expected that exposures to siponimod will occur in unintended pregnancies. Although more than half of all pregnancies in the US are unintended ([Henshaw, 1998](#)), the possibility of confounding by age, race, and other demographic variables will be considered. For example, the rate of unintended pregnancies is higher among low-income women/families than among other socioeconomic groups. It is possible that demographic variables will be associated with treatment as well. As such, these factors will be taken into consideration in the recruitment of comparison groups and in the analysis.

It is not possible to predict the number of pregnancy exposures that will occur for a newly marketed medication, and therefore, sample size is based on estimates that may require revision as the study progresses. Although all possible measures will be taken to ensure registry awareness and outreach including marketing via websites, social media, print media, scientific conferences, etc., it is known that enrollment rates, particularly in MS pregnancy registries, have been poor ([Krueger et al, 2017](#), [Gelperin, et al 2016](#)). Pregnancy registry enrollment rates are subject to drug utilization among pregnant women. Drugs with relatively low use among pregnant women ( $\leq 20/100,000$  live birth pregnancies) had less successful enrollment in pregnancy registries ([Bird et al, 2017](#)). In this study, we have proposed a sample size that accounts for operational feasibility, thereby ensuring generation of data that will provide insights into effects of siponimod on pregnancy outcomes to the patients and prescribers in a timely manner.

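### The 1:1:1 ratio and monthly count-balance rule give no direction, so they can be read as slowing comparator enrolment below the planned 289 if exposed women are scarce

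*Protocol*

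**What the plan says.** The Abstract (Study size) gives each cohort its own target. For the disease-matched cohort this is "289 pregnant women diagnosed with MS not exposed to siponimod during pregnancy (primary comparison group/comparison group 1"), and the exposed and healthy cohorts have the same figure. Section 7.5.1 puts the total as "approximately 867 pregnant women will be enrolled in US and Canada with a ratio of 1:1:1".

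Section 7.5 adds an operating rule: "Balance in the cohort numbers will be monitored on a monthly basis, and overall balance addressed by adjusting recruitment activities as needed". It concerns counts, is applied throughout accrual, and names neither the cohort to be adjusted nor the direction.

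On accrual the protocol gives two figures. Section 7.2 says that "approximately 17-18 pregnant women with exposure to siponimod could be enrolled in the Registry each year". Section 7.5 says "Recruitment goals are set at an average of 34-36 subjects per year in each of the 3 groups", and Table 7-3 sets this out year by year. Section 7.2.1 states: "There will be 7 years of active recruitment". Section 7.9 concedes that "it is known that enrollment rates, particularly in MS pregnancy registries, have been poor".

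Table 7-4 gives 80% power at a relative risk of 3.0 with 231 live-birth pregnancies per group and a 3% comparator rate. Its footnote reads "All tests are two-sided with alpha = 0.05, based on Fisher's exact test, unless specified otherwise".

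**The concern.** The supply of exposed pregnancies depends on how much the drug is used by women who become pregnant, which the registry controls only in part. If exposed accrual falls short and outreach cannot raise it, the only way left to restore equal counts is to slow the comparators. A coordinating centre applying the monthly rule literally could do that in good faith, and nothing in the protocol tells it to continue to 289.

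The protocol gives no analytic reason for equal counts. The primary analysis uses inverse probability weighting on a propensity score (7.7.3.1.1), which balances covariates and does not need equal group sizes. Table 7-5 itself foresees an unequal comparison of 231 with 462. Precision given up this way cannot be regained at the analysis stage, because the women would not have been enrolled.

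**Working it through.** **Inputs.** Target 289 per cohort (Abstract). Losses of 10% spontaneous abortion or stillbirth, 5% elective abortion and 5% lost to follow-up, 20% in all (7.5.1). Comparator rate 3%, so 9% in the exposed at a risk ratio of 3.0; two-sided alpha 0.05 (Table 7-4). Exposed accrual 17-18 a year (7.2); 7 years of recruitment (7.2.1). The text of 7.5.1 quotes a detectable risk ratio of 4.4; I use the 3.0 of Table 7-4 and the Abstract.

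**The plan's own figure.** 289 × 0.80 = 231, as stated. The arcsine approximation is power = Φ(h·√[n₁n₂/(n₁+n₂)] − 1.96), with h = 2·arcsin√0.09 − 2·arcsin√0.03 = 0.261. For 231 v 231: 0.261 × √115.5 = 2.81; 2.81 − 1.96 = 0.85; Φ = 80.2%. This reproduces Table 7-4. Exact Fisher power, the test named in the footnote, is 74.0%. Both are shown below.

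**Exposed numbers at the 7.2 rate.** 17.5 × 7 = 122.5 enrolled; × 0.80 = 98 live-birth pregnancies. The range for 17 to 18 a year is 119-126 enrolled and 95-101 live births.

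**Comparator numbers.** Strict 1:1 gives 98. The planned 289 gives 231. Table 7-3 sums to 34 + 6 × 36 = 250 exposed, 250 disease-matched and 3 × 34 + 4 × 36 = 246 healthy women, not 289; 250 × 0.80 = 200.

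| Exposed v disease-matched live births | Fisher | Arcsine |
|---|---|---|
| 231 v 231 (as planned) | 74.0% | 80.2% |
| 98 v 231 (comparator reaches 289) | 55.4% | 58.2% |
| 98 v 200 (comparator reaches 250) | 54.9% | 56.3% |
| 98 v 98 (strict 1:1) | 31.7% | 44.8% |

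**Splitting the loss.** Exposed shortfall alone: 74.0 − 55.4 = 18.6 points by Fisher; 80.2 − 58.2 = 22.0 by arcsine. Additional loss if comparators are held at 1:1: 55.4 − 31.7 = 23.7 by Fisher; 58.2 − 44.8 = 13.4 by arcsine. The risk ratio detectable with 80% power moves from 3.88 (98 v 231) to 4.92 (98 v 98) by Fisher, and from 3.77 to 4.46 by arcsine.

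**Sensitivity.** Across 17-18 a year, Fisher power is 30-33% at 1:1 and 55-57% with 231 comparators. If recruitment ran 10 years at 17.5 a year (140 exposed live births), it is 47% against 66%.

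**The case against.** A reader might infer that the protocol requires comparators to be cut back when the exposed cohort lags. It does not. No section caps, pauses or slows comparator enrolment. Each comparator has its own target of 289 and its own yearly goals, and the 1:1:1 statement can be read simply as describing 867 = 3 × 289. Adjusting recruitment could equally mean more effort on exposed women, for whom 7.2.2.5 lists several routes. This stands, and it limits the point to what the rule permits.

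The low-accrual scenario also rests on one of two conflicting figures. At 34-36 a year the exposed cohort would roughly keep pace with the comparators and the rule would do little; at 231 v 231 the change has no effect. And the scenario is partly foreseen: 98 exposed live births lies just under the indicative 100 at which 7.7.4 considers discontinuation, 7.5 allows the sample size to be revised, and 7.5.1 contemplates pooling the comparators. These provisions deal with whether to continue or resize. None says what happens to comparator recruitment meanwhile.

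Nor should comparators be called cheap. Each woman involves interviews, record retrieval, an infant examination by a travelling examiner and a developmental questionnaire. Relative to strict 1:1, reaching 289 means about 289 − 122 = 167 more women per comparator cohort, though all are within the plan.

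**Conclusion.** The point holds as an ambiguity with a material downside. A count-balance rule with no stated analytic purpose and no direction can work against the protocol's own comparator targets in the accrual scenario that section 7.2 projects. If it were enforced strictly, the primary comparison would lose a further 13 points of power (arcsine) to 24 points (Fisher) at a risk ratio of 3.0.

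It would be wrong to conclude that keeping 289 comparators rescues the study. Power stays at 55-58%, and the gap from there to the planned figure is due to too few exposed women.

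The figures assume 7 years at 17.5 a year, 20% attrition in every cohort, first-trimester exposure in all exposed live-birth pregnancies, a 3% comparator rate, and an unweighted comparison; weighting would be expected to lower power. Strict 1:1 is the worst case, and a partial slowing would cost less.

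**What to change.** In 7.5 and 7.5.1, state that 1:1:1 is the enrolment target and not a running constraint. State also that each comparator cohort continues to its planned number and is not reduced to match a lagging exposed cohort, subject to the year-three feasibility decision in 7.7.4.

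In the same amendment, reconcile the 17-18 exposed women a year in 7.2 with the 34-36 a year in 7.5, and the Table 7-3 totals (250, 250 and 246) with 289. Reaching 289 in 7 years needs 289 / 7 = 41.3 women a year per cohort, which neither figure provides.

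No new rule on balance of characteristics is needed: 7.2.2.4 and 7.9 already monitor demographics, disease severity and gestational age at enrolment.

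The cost is protocol wording, with no women beyond the planned 289 per comparator cohort. There are two downsides. The planned comparator follow-up is paid for even if exposed accrual turns out low, and calendar time of enrolment may differ somewhat between cohorts.
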